3.6.3. Reporting Adverse Events

Adverse Events Reporting

Adverse events occurring (initial occurrence or a worsening of a pre-existing condition) after the informed consent has been signed and up to 4 weeks (28 days) after the last dose of study drug will be reported and included in the study database. However, pre-existing conditions detected as part of the screening procedures should be documented as medical history. Adverse events will be reported on the AE CRF page.

Serious Adverse Event Reporting

Reporting by Investigators

Detailed instruction regarding SAE reporting will be provided in the appropriate documents outside of this protocol. A brief, non-all-inclusive summary is provided below.

Any SAE experienced by a study subject after signing the informed consent to 28 days after the last dose of study drug will be reported to the Sponsor or designee. Additionally, SAEs that occur after this period will also be reported to the Sponsor or designee if the Investigator considers the SAE related to the study drug.

Serious adverse events (both initial reports and follow-up information) must be reported to the Sponsor or designee within 24 hours of the Investigator's (site's) awareness or notification of the event.

The Investigators should make every effort to provide complete information when reporting the SAE (both for initial reports, as well as for follow-ups).

The Investigator must continue to follow the subject until the SAE has subsided, the condition becomes chronic in nature, stabilizes (in the case of persistent impairment), or the subject dies. Within 24 hours of receipt of follow-up information, the Investigator must submit it to the Sponsor or designee.

The Investigator is also required to submit SAE reports to the IRB/IEC in accordance with local requirements. All investigators involved in studies using the same IMP will

receive any Suspected Unexpected Serious Adverse Reaction (SUSAR) reports for onward submission to their local IRB/IEC as required. All reports sent to investigators will be blinded.

Reporting by the Sponsor

Competent authorities and IRBs/IECs will be informed by the Sponsor or designee of SUSARs according to the local requirements. Additionally, all SUSARs will be reported by the Sponsor or designee into the EudraVigilance system, as appropriate. Cases will be unblinded by designated personnel for reporting purposes as required.

Exposure in Utero Reporting:

If a female subject becomes pregnant or the female partner of a male subject participating in the study becomes pregnant after the subject receives the first dose of study drug, or within 28 days of discontinuing study drug, the Investigator should report the pregnancy to the Sponsor or designee within 24 hours of being notified.

The subject/partner should be followed by the Investigator until completion of the pregnancy. If the pregnancy ends for any reason before the anticipated date, the Investigator should notify the Sponsor or designee. At the completion of the pregnancy, the Investigator will document the outcome of the pregnancy. If the outcome of the pregnancy meets the criteria for immediate classification as an SAE (i.e., spontaneous abortion, stillbirth, neonatal death, or congenital anomaly), the Investigator should follow the procedures for reporting an SAE as described above.

Overdose Reporting:

An overdose is a significant variation from the recommended/scheduled dosage for a product. For the purposes of this study, overdose is defined by any confirmed use of blinded study medication of more than four tablets once a day. If such situations occur, the Investigator should provide additional training to the subject on study drug dosing instructions and emphasize the importance of compliance. Currently there is no known antidote to JTE-051, thus appropriate symptomatic and/or supportive care is to be provided at the Investigator's discretion, as needed. The subject's continued eligibility will be left to the judgment of the Investigator.

[figure not shown]
Information on overdoses in subjects is collected by the Sponsor or designee. Should a subject experience an overdose during the course of the study, the investigator or qualified designee must report the overdose as soon as possible, but not later than the timeframe requested by the Sponsor or designee after the investigator or qualified designee first becomes aware of the overdose. Instructions will be provided on how to collect this information.

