3.3.1. Inclusion Criteria

1. Males and females, 18 to 75 years of age (inclusive) at the Screening Visit (Visit 1);
2. A diagnosis of RA prior to the Screening Visit, based on the ACR/EULAR 2010 Classification Criteria²³ (see [Appendix 1](#));
3. Active disease despite ongoing therapy with up to 2 non-biologic DMARDs, including MTX at both the Screening and Baseline Visits (Visit 1 and Visit 2), as defined by both:
 - a. ≥ 6 out of 68 tender joints **AND**
 - b. ≥ 6 out of 66 swollen joints;
4. Screening hs-CRP $\geq 1.2 \times$ ULN, based on the central laboratory values;
5. Background treatment with up to 2 non-biologic DMARDs, including MTX (mandatory) and one of the following medications (optional): sulfasalazine ≤ 3 g/day, hydroxychloroquine ≤ 400 mg/day or chloroquine: ≤ 250 mg/day, at the time of the Screening Visit (Visit 1);
 - The MTX dose must be 15-25 mg/week (or the maximum documented tolerated dose for the subject, not <10 mg/week) and all background therapy must be stable, defined as no change in dose or route of administration for ≥ 12 weeks prior to the Randomization Visit (Day 1). See Section [3.5.4.1](#) for all concomitant medication-related restrictions.
6. Body Mass Index (BMI): 18 to 40 kg/m^2 (inclusive) at the Screening Visit (Visit 1);
7. Females may participate if they meet one of the following criteria:
 - Surgically sterile (e.g., hysterectomy or bilateral oophorectomy), or
 - Post-menopausal (i.e., history compatible with menopause [i.e., reported lack of menses for ≥ 12 months prior to Visit 1] and no other biological/surgical cause AND a serum follicle-stimulating hormone (FSH) measurement of ≥ 40 mIU/mL at Visit 1), or
 - Of childbearing potential and are compliant with at least 2 acceptable forms of birth control (in conjunction with their partner) for the duration of the study and for at least 12 weeks after the last dose of study drug. Acceptable contraceptive methods include the following: intrauterine devices; partner sterilization (with the

appropriate post-vasectomy documentation of the absence of sperm in the ejaculate); condom with a spermicide; diaphragm, cervical cap, vaginal sponge, or “female condom”, all with spermicide;

Notes:

- Females with sterilization history limited to tubal ligation will be considered of childbearing potential and must comply with the contraception regimen as described above.

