- Females with a history compatible with menopause and have a serum FSH <40 mIU/mL at Visit 1 will be considered of childbearing potential and must agree to comply with a contraceptive regimen as described above.
- Concomitant use of a female condom and a male condom is not considered an acceptable method of contraception for the study.

8. Males with female partners of childbearing potential must agree to practice total abstinence or to utilize a barrier contraceptive method with spermicide for the duration of the study and for at least 12 weeks after the last dose of study drug; additionally, male subjects must not donate sperm for the duration of the study and within 12 weeks of the last dose of study drug;

- Female partners of male subjects randomized in this study must be surgically sterile, postmenopausal, or use an acceptable form of birth control (see description listed in inclusion criterion # 7; additionally, oral and implantable hormonal contraceptives are considered acceptable in female partners of male subjects) for the duration of the study and for at least 12 weeks after completing the study;

9. Able and willing to give written informed consent.

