Note: Subjects with Sjögren's syndrome secondary to RA are permitted in the study provided that all other inclusion/exclusion criteria are met;
18. History or presence of any lymphoproliferative disorder, such as Epstein Barr Virus-related lymphoproliferative disorder, lymphoma, leukemia, multiple myeloma, etc., or signs and symptoms suggestive of current lymphatic disease, such as Hodgkin's or Non-Hodgkin's lymphoma;
19. History of or current malignancies with the exception of adequately treated or excised non-metastatic basal cell or squamous cell carcinoma of the skin or cervical carcinoma in situ >6 months prior to the Screening Visit (Visit 1);
20. History of organ transplantation;
21. Acute coronary syndrome (e.g., myocardial infarction or unstable angina), percutaneous coronary intervention (Percutaneous Transluminal Coronary Angioplasty [PTCA] or similar procedures), coronary artery bypass graft (CABG) surgery, cerebrovascular accident or transient ischemic attack (TIA) within 6 months prior to the Screening Visit (Visit 1);
22. Any history or presence of Class III or IV heart failure, as defined by the New York Heart Association (NYHA)²⁴ or known Rutherford category 4 or higher peripheral arterial disease;
23. Any history or presence of clinically significant arrhythmias or other ECG abnormalities, according to the Investigator's judgment;

24. Uncontrolled arterial hypertension defined as repeated (i.e., up to 3 repeat measurements are allowed) systolic blood pressure ≥ 160 mmHg or diastolic blood pressure ≥ 100 mmHg at the Screening Visit (Visit 1);

32. Pregnant or nursing females at Screening Visit or Day 1 (Visit 1 and Visit 2) or subjects who plan to become pregnant or initiate breastfeeding during the study and within 12 weeks after the last dose of study drug;
33. Significant history of drug or other hypersensitivities (e.g., multiple drug allergies or severe allergic reactions, including angioedema);

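### On its natural reading, the pregnancy reporting rule ends 28 days after study drug is stopped, while the protocol's own pregnancy precautions run for at least 12 weeks after the last dose

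*Protocol*

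**What the plan says.** The pregnancy rule is in Protocol section 3.6.3, under the in utero exposure heading. Its trigger is that a female subject, or the female partner of a male subject, "becomes pregnant after the subject receives the first dose of study drug, or within 28 days of discontinuing study drug". Two duties follow. On timing, "the Investigator should report the pregnancy to the Sponsor or designee within 24 hours of being notified". On outcome, "The subject/partner should be followed by the Investigator until completion of the pregnancy".

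The precautions against pregnancy are set elsewhere and run longer:

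- Section 3.3.1, criteria 7 and 8: contraception by women of childbearing potential, and contraception or abstinence by men with partners of childbearing potential, during the study and "for at least 12 weeks after the last dose of study drug".
- Section 3.3.1, criterion 8: "male subjects must not donate sperm for the duration of the study and within 12 weeks of the last dose of study drug".
- Section 3.3.1, criterion 8, for female partners of male subjects: sterility, menopause or birth control "for the duration of the study and for at least 12 weeks after completing the study".
- Section 3.3.2, criterion 32, excludes "subjects who plan to become pregnant or initiate breastfeeding during the study and within 12 weeks after the last dose of study drug".

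Section 3.6.3 also has a late-event rule. After the 28-day SAE window, "SAEs that occur after this period will also be reported to the Sponsor or designee if the Investigator considers the SAE related" to study drug.

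**The concern.** Contraception and pregnancy reporting deal with the same event. One tries to prevent it, and the other documents it when prevention fails. Here the second ends well before the first. A contraceptive failure in the later part of the protocol's own precaution period could come to the site's attention without prompting a report or a record of how the pregnancy ended.

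What is at stake is safety information. Section 1.3 describes this as the first study of the compound in patients, so each known pregnancy outcome has some value.

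**Working it through.** The plan gives no figure to reproduce. The check compares the windows in days after the last dose, taking discontinuation of study drug and the last dose as the same day.

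**Inputs**

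- Pregnancy reporting window: 28 days (section 3.6.3).
- Precaution window for subjects: 12 weeks × 7 = 84 days (section 3.3.1, criteria 7 and 8; section 3.3.2, criterion 32).
- Follow-up Visit (Visit 7): about four weeks, or 28 days, after the last dose (section 3.5.3).

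**Step 1: how the trigger reads.** Taken literally, its first limb (pregnancy after the first dose) has no end date, so every later pregnancy would qualify. The 28-day limb would then do nothing. The natural reading is one window, from first dose to 28 days after stopping. The trigger is when the pregnancy begins, and the 24-hour clock starts at notification. A pregnancy that begins by day 28 but is discovered later is therefore covered. The question concerns only pregnancies that begin after day 28.

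**Step 2: gap for subjects.** 84 − 28 = 56 days (days 29 to 84). As a share of the precaution period, 56 / 84 = 66.7%.

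**Step 3: gap for partners of male subjects.** Criterion 8 counts the partner's 12 weeks from completion of the study, which it does not define.

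- If completion means the last dose: 84 − 28 = 56 days, as in step 2.
- If completion means Visit 7: the window ends at about 28 + 84 = 112 days, and the gap is about 112 − 28 = 84 days (84 / 112 = 75%). This is approximate because the timing of Visit 7 is approximate.

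**Step 4: other routes to a report.** The late-SAE rule reaches serious events that the investigator considers related. A congenital anomaly is an SAE under section 3.6.1, and the pregnancy text also sends spontaneous abortion, stillbirth and neonatal death to the SAE procedures. The late-SAE rule does not require a report of the pregnancy itself, and it does not require follow-up to an outcome. The sentence before it speaks of study subjects. The late-event sentence does not repeat that limit, so its reach to partners is unclear. The last scheduled pregnancy test is at Visit 7 (section 3.5.6.17), so later pregnancies would be known only if someone tells the site.

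**Step 5: who is affected.** Criterion 7 places no contraception duty on surgically sterile or confirmed post-menopausal women, and criterion 8 concerns partners of childbearing potential. Entry runs to age 75. The affected number is therefore smaller than the planned 250, and the documents do not allow it to be estimated.

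**The case against.** The strongest reply is that the two windows serve different purposes and need not match. The 28 days agree with the AE and SAE windows in section 3.6.3 and with the four-week follow-up. Other precautions outlast 28 days too: exclusion criterion 12 bars live vaccination for 6 weeks after the last dose. Section 1.3 calls the four-week follow-up conservative on pharmacokinetic grounds, and the text after that is redacted. The documents do not explain why 12 weeks was chosen for contraception. Serious outcomes judged related already have a route to the sponsor with no end date. The consent pages are not available, so subjects may already be asked to report later pregnancies.

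Much of this stands. There is no contradiction between rules, and the visible text cannot show that 28 days is too short. A reader might infer that fetuses are exposed to drug without surveillance after day 28. The documents do not support that inference: nothing visible shows exposure that late, and the one visible remark on the interval points the other way.

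Two parts of the reply do not dispose of the point. The late-SAE rule leaves out normal outcomes and events judged unrelated. Section 3.6.3 does say that its SAE text is an incomplete summary of instructions held elsewhere, but that remark introduces SAE reporting and does not mention pregnancy, for which the section states its own window. If the sponsor has pharmacokinetic or toxicological grounds for 28 days, stating them would also settle the matter.

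**Conclusion.** The point holds as a minor mismatch between windows. A known pregnancy that begins on days 29 to 84 after the last dose has no visible duty of report or outcome record, apart from serious events judged related. The size is 56 of 84 days for subjects. For partners it is 56 days or about 84 days, depending on what completion of the study means. These are calendar gaps and do not measure risk.

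The conclusion rests on reading the 28-day clause as a limit. If the sponsor meant the rule to be open-ended, there is no gap, but the sentence still needs rewording.

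Two wider readings should be resisted. The gap does not touch all 250 subjects, for the reason in step 5. It also does not lose pregnancies that begin inside the 28 days and are notified late. The documents give no basis for a count of cases, which is expected to be very small. Efficacy analyses, power and the SAP analyses are unaffected.

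**What to change.** In the pregnancy paragraph of Protocol section 3.6.3, replace the 28-day limit with a limit of 12 weeks after the last dose of study drug, worded as a single window that starts at the first dose. For partners of male subjects, tie the window to inclusion criterion 8, and state there whether study completion means the last dose or Visit 7. At Visit 7, ask subjects to notify the site of any pregnancy, their own or a partner's, that begins in that window.

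The cost is one wording change, one definition, one instruction at an existing visit, and a few extra reports and outcome follow-ups. No visit or test is added. Capture would depend on subjects notifying the site, so it would be incomplete.

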3.7. Identification of Treatments

3.7.1. Method of Assigning Subjects to Treatment Groups

At the Screening Visit (Visit 1), each site will assign potential study subjects an eight-character subject number. This number will consist of a four-digit site number (with the first two digits representing the country-specific number and the next two digits representing the site-specific number) and a three-digit subject number assigned in a sequential manner. The hyphen between the site and subject number will account for the eighth character. This number will represent the subject's identifier throughout the study. Following confirmation of eligibility at Visit 2, the Interactive Web Response System (IWRS) will be contacted by the site and it will assign the subject a four-digit randomization number that will correspond to a randomly assigned treatment group.

3.7.2. Identity of Investigational Products

3.7.3. Storage and Handling Procedures

The JTE-051 and placebo tablets should be stored at room temperature between 20 and 25°C (United States Pharmacopeia [USP]) and in a secure location with restricted access.

3.7.4. Clinical Supplies Packaging

Each site will receive a supply of double-blind study drug packaged as blister cards corresponding to 8 days of QD dosing. Each blister card will contain a total of 32 JTE-051 tablets.

Study drug blister cards may be labeled with the following information, as appropriate:

- Sponsor identity and protocol number
- Card number
- Dosing instructions
- Spaces for site personnel to add subject number and subject initials

- Spaces for site personnel to add visit number, site number, and Investigator name
- Spaces for site personnel to add the card identifier, as appropriate
- Quantity and identity of contents
- Lot number and storage conditions
- Expiration date
- For investigational use only statement

The planned blister card allocation of tablets for each dose, broken down by treatment group, is provided below.

Treatment Group	Tablet 1	Tablet 2	Tablet 3	Tablet 4
JTE-051 50 mg	JTE-051 50 mg	JTE-051 Placebo	JTE-051 Placebo	JTE-051 Placebo
JTE-051 100 mg	JTE-051 50 mg	JTE-051 50 mg	JTE-051 Placebo	JTE-051 Placebo
JTE-051 150 mg	JTE-051 50 mg	JTE-051 50 mg	JTE-051 50 mg	JTE-051 Placebo
JTE-051 200 mg	JTE-051 50 mg	JTE-051 50 mg	JTE-051 50 mg	JTE-051 50 mg
Placebo	JTE-051 Placebo	JTE-051 Placebo	JTE-051 Placebo	JTE-051 Placebo

3.7.5. Administration of Study Drug

During the Treatment Period, beginning on the day of Visit 2, subjects will self-administer one dose of study drug (4 tablets) daily for 12 weeks. Study drug will be taken once daily in the morning, regardless of meals. On the day of scheduled study visits, subjects should not take study drug prior to arriving to the study site. At the site, study drug will be administered from the previously supplied non-back-up blister card, if available, after all study procedures have been completed. If no tablets from the previously supplied non-back-up blister cards are available, then the subject should dose from the new non-back-up blister card supplied at that visit. The back-up study drug blister card should only be utilized by subjects if all study drug from the regularly-supplied (non-back-up) blister cards has been used.

Randomized subjects will receive two study drug blister cards at Visits 2 and 3, respectively. Subjects will receive four blister cards each on Visits 4 and 5. Additionally, at Visit 2, all subjects will receive a back-up blister card (identical in appearance with the other blister cards) for use as needed throughout the study. The back-up blister card may be identified at the site level and subjects will be instructed to utilize all tablets from the other (non-back-up) blister cards before initiating tablet use from the back-up blister card. The subjects will be instructed to return the clinical supplies (full, partially full, and empty blister cards, including the back-up blister card) at Visits 3, 4, 5 and 6 for accountability and compliance assessment. Following completion of accountability and compliance assessments, the back-up blister card will be re-dispensed at Visits 3 through 5 and will be collected at Visit 6 along with all non-back-up blister cards.

In the event that the subject does not take the study drug on a given day during the Treatment Period, the subject should not take more than the daily dosage on the following treatment day.

3.7.6. Management of Clinical Supplies

The Investigator will have responsibility for the control and proper distribution of all study drug (including any investigational product or reference product) in accordance with this protocol. The Investigator is responsible for ensuring that all study drug will be stored at the site at recommended storage temperatures and conditions, in a secured area, free of environmental extremes, with restricted access. The Investigator also ensures that all study drug will be dispensed only to study subjects who have provided written informed consent and have met all entry criteria.

Study drug accountability will be performed by the Investigator or designee at each study visit during the Treatment Period, according to the schedule of procedures presented in [Table 1](#). Study drug compliance will be assessed and documented per GCP.

3.7.7. Randomization

Approximately 250 eligible subjects with active RA will be randomized into this study. Subjects will be randomized in a 1:1:1:1:1 ratio (50 subjects per treatment group) to receive JTE-051 50 mg, JTE-051 100 mg, JTE-051 150 mg, JTE-051 200 mg or placebo once daily. Randomization will be stratified by region and by the screening hs-CRP level (the qualifying hs-CRP value must be utilized).

An IWRS will be employed for the randomization activities. It will use a stratified randomization algorithm that takes into account the strata specified above.

The randomization code will be controlled by an unblinded member of the Sponsor or designee who will provide the randomization code to select laboratories, see Section [3.7.8](#).

